epinephrine and inflamed and injured vasculature in the surgical field of burn patients. One study reported benefit and a favorable side-effect profile of 1:10,000 epinephrine-soaked gauzes applied prophylactically for hemostasis during laparoscopic cholecystectomy (77).

Potential Adverse effects of Endotracheally- and Endobronchially-Administered Topical Epinephrine

Data concerning the systemic effects of endobronchially administered epinephrine are limited. Adverse hemodynamic effects of topical epinephrine are attributed to systemic absorption of epinephrine from the airways into the pulmonary and bronchial circulatory systems. Two pharmacokinetic studies in a canine model explored blood concentrations of epinephrine after administration through the airways. Roberts et al. compared blood concentrations and hemodynamic effect of intravenous (IV) versus endotracheal (ET) instillation of epinephrine administered in doses of 0.005, 0.03, 0.06, and 0.09 mg/kg diluted in 5 mL of normal saline. The authors reported that following ET installation, maximum blood concentrations of epinephrine were approximately one-tenth of those achieved with an equal dose administered IV. Interestingly, while IV administered epinephrine was rapidly metabolized and cleared, ET administration was characterized by a more sustained blood concentration. The same relationship between IV and ET administration was observed when comparing pharmacological effects with the ET route requiring ten times the IV dose in order to result in a significant increase in blood pressure (78). Mazkereth et al. demonstrated significant measurable systemic levels when epinephrine in a dose of 0.02 mg/kg diluted in 2 mL of saline was administered into the airways using a catheter. More than a 4-fold increase in systemic levels was achieved when epinephrine was installed into the distal airways via a catheter as compared with when it was administered into the trachea (maximal concentration 8.9 ± 3.2 vs. 2.0 ± 0.4 ng/mL). However, neither group demonstrated any significant change in the heart rate, and both had similar, minor decreases in blood pressure for 2 to 5 minutes with no significant differences in arterial blood gases (79). It is noteworthy that the dose range of epinephrine utilized in the aforementioned studies exceeds the dose used for achievement of hemostasis in TBLB-related hemorrhage by a factor of 4 to 10.

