- 5.12. Any history of critical ischemia related to peripheral arterial disease.
- 5.13. Persistent resting heart rate (HR) measurement of ≥ 120 beats per minute prior to or at the time of the procedure.
- 5.14. Persistent resting systolic blood pressure (SBP) measurement of ≥ 180 mm Hg prior to or at the time of the procedure.
- 5.15. Persistent resting diastolic blood pressure (DBP) measurement of ≥ 110 mm Hg prior to or at the time of the procedure.
- 5.16. History of acute closed-angle glaucoma within one year of the procedure.
- 5.17. Diagnosis of pheochromocytoma requiring pharmacologic therapy with an alpha adrenoreceptor blocker at the time of the procedure.
- 5.18. Diagnosis of thyrotoxicosis requiring pharmacologic therapy with an anti-thyroid agent at the time of the procedure.

Recruitment Strategy

Recruitment for the proposed clinical trial will follow the well-established procedures at UMMC. Patients will be recruited from the daily clinical practice of the study investigators as well as the patient cohort being followed and treated by the lung transplantation service in our institution. As a referral center for lung transplantation in the state of Maryland as well as the surrounding states, UMMC care for a large number of post-lung transplantation patients who are likely to meet inclusion and exclusion criteria. Based on our experience with regard to our local practice over past years, we are fairly confident we have access to adequate numbers of patients and procedures in order to complete recruitment. This provides reasonable assurance that a sufficient number of participants should be able to be recruited and a sufficient number of procedures should be able to be recorded for this trial as well as speaks to its clinical and scientific relevance as its conduct will provide important information in the role of prophylactic epinephrine as means to prevent pulmonary and airway bleeding in lung transplant recipients undergoing bronchoscopic TBLB.

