3. Acute closed angle glaucoma within 30 minutes of the instillation of the study drug.
4. New onset ECG changes suggestive of myocardial ischemia, including ST segment changes (defined: ≥ 1 mm ST segment elevation or ≥ 3 mm ST segment depression in ≥ 2 precordial or limb ECG leads that correspond together to one of the cardiac walls), new onset ventricular tachycardia, significant increase (≥ 10 per minute) in occurrence of ventricular ectopic beats, new onset supraventricular arrhythmia, new onset bundle branch block, and new onset 2nd or 3rd degree atrioventricular block, all occurring within 30 minutes of the instillation of the study drug.
5. Significant change in heart rate (defined as heart rate of >120 bpm and/or increase by ≥ 30 bpm above the baseline or heart rate <60 bpm and/or ≥ 30 bpm below the baseline) as recorded within 30 minutes of the instillation of the study drug.
6. Significant change in systolic blood pressure (defined as increase in systolic blood pressure >180 mm Hg and/or ≥ 40 mm Hg above the baseline; increase in diastolic blood pressure >110 mm Hg and/or ≥ 20 mm Hg above the baseline; or fall in systolic blood pressure <90 mm Hg and/or ≥ 20 mm Hg below the baseline) as recorded within 30 minutes of the instillation of the study drug.

Please refer to the section titled “Adverse Events Reporting and Data Monitoring” for further elaboration regarding reporting adverse events to the study monitoring committee. Please refer to the section titled “Adverse Events Reporting to the IRB” for further elaboration regarding reporting adverse events to the IRB.

Immediate Post-Procedure Surveillance

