Data are expressed as means with standard deviations, medians with interquartile range, percentages, and proportions as appropriate. Continuous outcome variables were visually examined for normality and outliers using histograms and scatter plots. The normal distribution was assessed with the Shapiro-Wilk test. Continuous variables were compared with the Student's t-test for normally distributed data with similar variance and the Mann-Whitney tests for non-normally distributed data. Proportions were compared using Chi-squared or Fisher's exact tests as appropriate. Statistical significance was set at $P<0.05$. All statistical analyses were performed based on original assigned groups and using Stata software, version 14 (Stata Corp LLC).

Potential Benefits

We hypothesize that prophylactic instillation of topical epinephrine prior to TBLB will reduce procedure-related hemorrhage, leading to lower rate of prematurely aborted procedure due to bleeding complications and higher yield of intended biopsies. The participants may, therefore, have direct benefit from participation if prophylactic topical epinephrine reduces the rate of procedure related hemorrhage in TBLB therefore avoiding early termination of procedure and more intended biopsies taken providing a higher diagnostic yield.

No financial reimbursements or incentive for participating in the PROPHET study will be provided.

Potential Risks and Discomforts

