The decision to perform bronchoscopy with TBLB will be based on clinical indications as a part of each study participant standard of care and not as a part of the research. Potential risks and discomfort of the bronchoscopy and TBLB themselves are no more than what the participant would undergo as a part of their post-transplantation bronchoscopy. These risks include hemorrhage related to the procedural maneuvers, respiratory distress, pneumothorax (i.e. collapsed lung). These complications are rare (less than <1% of all bronchoscopies) and can be expected in any bronchoscopy and TBLB. An experienced bronchoscopist and a well-trained staff such as ours are well trained to handle these potential complications in the controlled environment of the bronchoscopy suite. Bronchoscopic procedures performed in the UMMC bronchoscopy suite are usually performed under conscious sedation. Potential risks and discomforts of conscious sedation for our study participants are no more than what the participant would undergo for their post-transplantation bronchoscopy. Conscious sedation is generally safe, but can cause nausea and vomiting, ineffective ventilation resulting from airway obstruction or respiratory depression, causing hypoxia, hypercarbia, or aspiration associated with loss of protective airway reflexes, as well as cardiovascular complications including hypotension and arrhythmia. Drug overdose and drug reactions are a constant possibility in patients undergoing conscious sedation.

The potential risks of epinephrine are well described in cases of sufficient systemic absorption of the drug. Most serious complications are arrhythmias and hemodynamic compromise and tend to occur in a dose dependent manner. Most complications seen are in the setting of existing bleeding from procedural maneuvers. Topical epinephrine, in these situations, is instilled in airways with damaged mucosa and blood vessels. There is direct communication between the airway and blood vessels allowing for more direct absorption of epinephrine leading to higher concentration of epinephrine in the blood stream and therefore systemic complications. There²⁶ is no reported data of the incidence rate of complications arising from epinephrine in the setting of topical prophylactic use, but it is expected to have lower rate of systemic absorption. In rare

cases of complications, our staff is well trained and the procedure room is equipped to treat these potential complications of epinephrine.

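### Safety outcomes 5 and 6 each count a rise or a fall as one event, so the by-arm comparison cannot show which direction differs and falls in both arms dilute a difference in rises

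*Combined protocol and SAP*

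**What the plan says.** Safety Outcomes, item 5, is one outcome. Its upper side reads "Significant change in heart rate (defined as heart rate of >120 bpm and/or increase by" at least 30 bpm; its lower side is joined on with "above the baseline or heart rate <60 bpm and/or" at least 30 bpm under baseline. Item 6 is headed as a change in systolic pressure. It is met by a systolic rise, by an "increase in diastolic blood pressure >110 mm Hg and/or" a stated rise over baseline, "or fall in systolic blood pressure <90 mm Hg and/or" a stated drop. Both items cover the 30 minutes after instillation.

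Aim 4 asks how often clinically significant haemodynamic changes occur, within an adverse event profile set against placebo; it names no direction. The Data Analysis section says "Proportions were compared using Chi-squared or" Fisher's exact tests, with significance at P<0.05. Neither that section nor Data Monitoring splits items 5 and 6 by direction, and no continuous heart-rate or pressure outcome is listed.

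On what to expect, Potential Risks and Discomforts says sedation can cause "cardiovascular complications including hypotension and arrhythmia". The background on airway epinephrine reports that in dogs given it by two routes, "both had similar, minor decreases in blood pressure for 2 to 5 minutes". The section on topical prophylaxis reports more tachycardia with epinephrine-soaked gauze in burn surgery.

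**The concern.** The documents give reasons to expect movement both ways, so watching both is sensible. The difficulty is that one yes/no event per item hides which way the patient moved. A small pooled difference could be read as reassuring although rises differ by arm. A pooled excess could be read as a pressor effect although it consists of falls.

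Two gaps in the definitions add to this. First, the baseline is not defined: it could be the intake vital signs or the last reading before instillation. A second airway may also be instilled (Procedure Performance, item 7), and the text does not say which instillation counts. Second, the lower side of item 5 lacks the word 'fall' that item 6 uses. Read literally, a patient already under 60 bpm scores an event without changing. The head word 'change' allows the opposite reading. The only numeric heart-rate exclusion is on the high side (5.13, "Persistent resting heart rate (HR) measurement of" 120 or more); 5.7 removes some slow-rate conditions but sets no lower rate limit.

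**Working it through.** The plan states no event rate, effect size or power for these outcomes, so there is no figure to reproduce. The check asks what pooling does under assumed rates.

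**Inputs**
- 100 procedures (Overview), allocated by coin toss (Study Group Randomized Assignment): about 50 per arm.
- Fisher's exact test at P<0.05 (Data Analysis); two-sided is assumed, as sidedness is not stated.
- Assumed rises: 5% placebo, 25% epinephrine. Assumed falls: equal in both arms, 10% to 50%.
- Procedures are treated as independent, although a patient may contribute more than one.

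**Formulas.** With rise rate r and fall rate f, the pooled rate is 1 − (1 − r)(1 − f) if the two are independent, and r + f if no procedure has both. Power is the sum, over all pairs of counts from 0 to 50, of the two binomial probabilities for pairs with Fisher p < 0.05.

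**Example, f = 20%, independent.** Placebo: 1 − 0.95 × 0.80 = 24%. Epinephrine: 1 − 0.75 × 0.80 = 40%. The 20-point difference in rises becomes 16 points.

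| Falls, both arms | Pooled rates, independent | Difference | Power | Pooled rates, no overlap | Power |
|---|---|---|---|---|---|
| none (rises alone) | 5% vs 25% | 20 | 74.8% | 5% vs 25% | 74.8% |
| 10% | 14.5% vs 32.5% | 18 | 48.8% | 15% vs 35% | 56.8% |
| 20% | 24% vs 40% | 16 | 32.7% | 25% vs 45% | 47.7% |
| 30% | 33.5% vs 47.5% | 14 | 23.8% | 35% vs 55% | 46.2% |
| 40% | 43% vs 55% | 12 | 18.3% | 45% vs 65% | 46.2% |
| 50% | 52.5% vs 62.5% | 10 | 13.3% | 55% vs 75% | 47.7% |

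With no overlap the 20-point difference survives intact and the loss is in precision.

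**Smaller effect.** For rises of 5% vs 15%, power is 24.4% alone and 14.5% to 5.8% pooled with equal independent falls of 10% to 50%. Sample size is then the main limit, split or not.

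**Direction cannot be recovered.** The pooled 24% vs 40% above comes from a difference in rises alone. The same pair arises if rises are 5% in both arms and falls are 20% on placebo and 1 − 0.60/0.95 = 36.8% on epinephrine: 1 − 0.95 × 0.632 = 40%. The composite is identical; the clinical meaning is opposite.

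**The case against.** The strongest reply is that the plan never says the components will be shown only as one pooled event. Each direction has its own threshold, and nothing forbids a split. That is true: the gap is in what is specified beforehand, and the underlying readings exist. It remains a gap, because the outcomes are defined as single events, and a split chosen after unblinding carries less weight than one written in advance.

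A reader might go further and infer that pooling will cancel or reverse a true difference in rises. The arithmetic allows it. With rises of 5% vs 15% and falls of 30% vs 15%, the pooled rates are 1 − 0.95 × 0.70 = 33.5% and 1 − 0.85 × 0.85 = 27.75%, a difference of −5.75 points. But this needs epinephrine to make falls rarer, and the documents do not suggest that; the canine study they cite reports small pressure decreases after airway epinephrine. Only dilution has a documented basis, namely hypotension under sedation.

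A reader might also expect the split to isolate the study drug. It does not. Topical epinephrine for bleeding is allowed in both arms at the operator's discretion and may fall within the 30 minutes. If placebo patients bleed more, that use could itself narrow a difference in rises.

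Finally, it is tempting to count an absolute threshold only when the baseline lay on its other side. That would redefine the composites and lose real deteriorations: a heart rate going from 58 to 35 bpm falls by 23, under the 30 required, and would no longer count. Such events should be flagged, not dropped.

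**Conclusion.** The point holds as a matter of definition and reporting. Items 5 and 6 each merge opposite movements, so a by-arm proportion cannot identify direction, and falls common to both arms weaken the contrast in rises. Under the assumed 5% vs 25% rises, power drops from 75% to 49%–13% if falls are independent of rises, and to 46%–57% if the two never coincide. All rates are assumptions, with 50 independent procedures per arm; repeat patients and coin-toss imbalance are ignored.

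Counting both directions is not itself a fault. The weight is minor to moderate: Aim 4 is exploratory, this is a pilot, and the component readings are taken anyway. The gain is a correct description by direction rather than a rescue of power.

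**What to change.** Keep both composites and all thresholds as they are, and add:

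1. Five rows by arm: heart-rate rise, heart-rate fall, systolic rise, diastolic rise and systolic fall, each with the difference and its 95% interval. Align the heading of item 6 with its diastolic content.
2. For these rows, define baseline as the last reading before the first instillation.
3. Flags, without dropping any event, for patients already beyond an absolute threshold at baseline, for a second instillation, and for topical epinephrine given for bleeding within the 30 minutes.
4. Optionally, baseline-adjusted peak and trough change in heart rate, systolic and diastolic pressure, from the continuous heart rate and the pressures taken every 3 minutes (Procedure Performance, item 3).

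No new test or visit is needed. The flags need clock times for instillation and for epinephrine given for bleeding. The list of recorded procedure data does not name these times, but the full-length video could supply them.

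The statistical cost is more exploratory rows: five, or eleven with the six peak and trough changes. If eleven independent rows were each tested at 5%, the chance of at least one false positive would be 1 − 0.95^11 = 43%. Report estimates with intervals and make no claim from a single row.

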Any potential PROPHET participants who meet initial screening criteria and are anticipated to undergo bronchoscopy with TBLB will undergo a thorough chart review conducted by a member of the research team. Demographics, past medical history and comorbid conditions, indication for lung transplant, indication for bronchoscopy with TBLB and possible concurrent procedure(s), prior complications related to bronchoscopy or TBLB, current and active medications, most recent pulmonary function tests, and most recent report of echocardiogram will be reviewed to ensure inclusion and exclusion criteria are met. Recent laboratory data including complete blood count, comprehensive metabolic panel, coagulation studies, and 12-lead electrocardiogram will be reviewed following our institutional standard protocol for bronchoscopy.

On the day of procedure, as per our institutional procedural protocol, participants will have intake vital signs obtained. Recent history and physical examinations dated within 30 days of procedure will be reviewed or obtained if not available. Participants will be monitored under telemetry starting with this intake period, during and approximately an hour after conclusion of procedure unless procedural complication merit additional closer monitoring.

Monitoring Subjects and Criteria for Withdrawal of Subjects from the Study

Before and after the procedure, on the procedure day, study participants will be monitored in the UMMC endoscopy peri-procedure suite (for outpatients) or in the admitting unit (for inpatients). An on-call pulmonary physician will be available to assist with any immediate issues. During the procedure, study participants will be monitored by the UMMC bronchoscopy suite nursing staff, the performing bronchoscopist, and any additional physicians participating in the procedure. We do not anticipate problems requiring withdrawal of patients from the PROPHET study once enrolled, other than by the patient's request. In the event a study subject elects to be withdrawn from the study and requests their data to be withdrawn as well, we will comply.

Study Drug and Placebo Preparation, Packaging, and Randomized Assignment

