3. Per local protocol, peri-procedurally and during the procedure, the patient's heart rate, electrocardiography rhythm strip, respiratory rate, and oxygen saturation will be monitored continuously. Blood pressure will be repeatedly measured every 3 minutes. Up to 6 liters of supplemental oxygen via nasal cannula will be given in order to maintain an oxygen saturation of >92%. A defibrillator as well as a resuscitation drugs and equipment are available at all times in the bronchoscopy suite.
4. Patient will undergo the procedure in the supine position on an adjustable bed. Premedication will be performed per local protocol, including inhalation of 5 mL of 4% lidocaine via a nebulizer. Gurgling of 2 to 4 mL of 2% liquid lidocaine (20-40 mg) for upper airway anesthesia may also be applied depending on the performing bronchoscopist's preference. Moderate sedation will be achieved with a combination of midazolam (maximal dose of 6 mg per procedure) and fentanyl (maximal dose of 300 mcg per procedure). Laryngeal and lower airway anesthesia during the procedure will be obtained with the use of 2 mL aliquots of 2% liquid lidocaine up to a cumulative liquid lidocaine dose of 400 mg. A bite block will be used for procedures performed through the transoral approach. For the transnasal approach, 2% viscous lidocaine will be applied with a cotton swab to the chosen nostril and nasal passage to allow easy advancement of the bronchoscope.
5. Bronchoscopy will be performed with an Olympus BF-1T160 or BF-1TH190 (Olympus, Tokyo, Japan) video bronchoscope under fluoroscopic guidance (OEC 9900 Elite Mobile C-arm, GE Healthcare, Chicago, Illinois, United States).
6. For the purpose of independent post-procedure analysis, the entire procedure from insertion of the bronchoscope into the airways until its final retraction will be video-recorded on DVD media and individually labeled without disclosing study arm assignment. DVDs will be stored with other individual patient study documents for later review. Access to the stored DVDs will be provided only to the PROPHET study research team.

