7. Prior to biopsy performance 2 mL of 1:10,000 diluted epinephrine followed by 8 mL of ambient room air or 2 mL of sterile saline solution followed by 8 mL of ambient room air as described in "Study Drug and Placebo Preparation" will be instilled into the target airway by the bronchoscopist. This process may be repeated once, should the performing bronchoscopist choose to perform additional biopsy passes through a different airway. If choose to do so, the same study drug will be instilled into both airways. Any additional biopsies performed, will be done without airway instillation of study drug.
8. Biopsies will be performed using brand bronchoscopic biopsy forceps as preferred by the procedure performer. For ACR, aim will be to obtain 5 to 8 adequate biopsies, preferably from

the lateral subsegment of either the right or left lower lobes to allow optimal visualization and minimize forshortening under fluoroscopy as well as to avoid as much as possible spillage of blood into uninolved lung segments in the event of biopsy-related hemorrhage as described above. For the evaluation of radiological findings, aim will be to obtain 4 to 8 adequate biopsy specimens from an involved segment in one of the lungs based on imaging. All bronchoscopies will be performed by an experienced bronchoscopist.

9. The following data will be recorded with regard to the performance of the procedure:
 - 9.1. Patient study-arm assignment – recorded in a separate database.
 - 9.2. Indication for bronchoscopy with TBLB.
 - 9.3. Target number of TBLB specimens and target lobe and segment.
 - 9.4. Name and dosages of all medications administered to the patient in the hospital during the day of the procedure, including medications frequently administered during bronchoscopy such as topical anesthetic agents, sedation and analgesia agents, and hemostatic agents. Study drug vs. placebo administration will be recorded as described previously under “*Randomization*” and “*Study Drug and Placebo Preparation and Packaging*”.
 - 9.5. Supplemental oxygen requirements which exceed patient’s baseline requirements during or following the procedure.
 - 9.6. Any hemodynamic, cardiac, or respiratory events as recorded by telemetry in the procedure suite and/or in the recovery suite following the procedure.
 - 9.7. Bronchoscope model, including outer diameter and inner diameter of working channel.

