 - 9.8. Date and time of scope insertion and completion of the procedure as defined by the performing bronchoscopist.
 - 9.9. Biopsy forceps brand, including outer diameter, open forceps diameter, and type of forceps (round cup, oval cup, alligator, impaling needle).
 - 9.10. Fluoroscopy time.
 - 9.11. Number of forceps passes.
 - 9.12. Total number of acquired biopsy specimens; Specimen distribution across laboratories (anatomic pathology, microbiology, other laboratory).
 - 9.13. Lobe and segment of each biopsy specimen.
 - 9.14. Any medical intervention performed in the bronchoscopy suite or in the recovery suite for stabilization of the patient’s medical condition during or following the procedure, including hemostasis, management of cardiac events, and management of respiratory events.

Outcome Measures

Primary Efficacy Outcome

The primary efficacy outcome of the PROPHET Study is the prevalence of major hemorrhage as defined by two independent reviewers who will review the procedure video while blinded to the individual patient information, study drug assignment, and any procedure related data not recorded on video. Hemorrhage will be graded according to a grading system suggested by

Pilarczyk *et al.* (43) and modified in accordance with the PROPHET Study scientific question as follows:

Grade	Description
No hemorrhage	No hemorrhage
Minor	Endobronchial hemorrhage resulting in segmental or more distal bronchus blood spillage
Intermediate	Endobronchial hemorrhage resulting in lobar bronchus blood spillage
Major	Endobronchial hemorrhage resulting in mainstem bronchus, more proximal blood spillage, or spillage into the uninvolved lung

Secondary Efficacy Outcomes

1. Occurrence of no, minor, or intermediate bleeding as defined by the independent reviewer.
2. Likert scale grading of bleeding by independent observer on a scale of 1 to 5:

1	2	3	4	5
Much less than usual for TBLB	Less than usual for TBLB	Usual for TBLB	More than usual for TBLB	Much more than usual for TBLB

3. Intra-procedural grading by the performing bronchoscopist according to procedure-related outcome as described by Ernst *et al.* and Herth *et al.* (31,44):

Grade	Description
No hemorrhage	No hemorrhage
Mild	Any bleeding originating from the biopsy target airway requiring wedging of the bronchoscope or “in and out” motion in order to achieve hemostasis

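### Safety outcome 5 can score an unchanged pre-drug heart rate as a significant change, and neither outcome 5 nor outcome 6 defines baseline, so a real drug effect can be diluted

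*Combined protocol and SAP*

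**What the plan says.** All references are to the combined protocol and SAP.

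- **Safety Outcomes, item 5.** The upper limb reads "Significant change in heart rate (defined as heart rate of >120 bpm and/or increase by" 30 bpm or more. The lower limb follows: "bpm above the baseline or heart rate <60 bpm and/or" 30 bpm or more below baseline. Readings within 30 minutes of instillation count.
- **Safety Outcomes, item 6.** The and/or structure and window are the same for blood pressure (SBP above 180, DBP above 110, SBP below 90, or a stated shift from baseline). Each limb, however, is introduced as an increase or a fall.
- **Safety Outcomes, item 4.** Most of the ECG findings must be of new onset. Item 5 has no such condition.
- **Exclusion Criteria, 5.13 to 5.15.** These begin with "Persistent resting heart rate (HR) measurement of" 120 or more, then cover persistent resting SBP of 180 or more and DBP of 110 or more. They apply before or at the time of the procedure. No exclusion sets a lower limit for heart rate or blood pressure.
- **Baseline.** Items 5 and 6 use the word without defining it. Under Initial Evaluation, "participants will have intake vital signs obtained" on the procedure day. Study Flow lists vital signs at -2 to -1 hours. Both precede sedation and scope insertion, and neither is tied to these outcomes. Under Procedure Performance, item 3, heart rate is continuous and "Blood pressure will be repeatedly measured every 3 minutes".
- **Timing.** Instillation into a second airway is allowed ("This process may be repeated once", Procedure Performance, item 7). Item 9.8 records "Date and time of scope insertion and completion of the procedure as defined by the performing bronchoscopist". No listed field times the instillation.

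**The concern.** An outcome called a change should not be met by a value that has not changed. Under item 5 as written, a patient at 56 bpm before and after instillation has an event in either arm. The introduction to Safety Outcomes describes these items as complications deemed related to epinephrine, so that unchanged rate would be listed as a drug complication, even after placebo.

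The relative limbs have a related weakness. If the intake or -2 to -1 hour reading serves as baseline, any shift that midazolam, fentanyl or scope passage produces before instillation counts towards the outcome.

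What is at stake is Aim 4, which explores whether the adverse event profile of epinephrine is not significantly different from placebo. Under that framing a non-significant comparison tends to be read as reassurance. Background events unrelated to the drug make such a result more likely when a real effect exists.

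**Working it through.** The plan gives no power, effect size or event rate for safety, so there is no figure of its own to reproduce. The sample size rests on feasibility (Sample Size and Power Calculations).

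**Inputs from the documents:** 100 procedures (Overview), taken as 50 per arm under coin-toss allocation; P<0.05 and chi-squared or Fisher's exact test (Data Analysis). **Assumptions:** two-sided testing, independent procedures, and every rate, mean and SD below.

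**Step 1. Can a pre-drug value meet the definition?** With normal heart rate, the share already below 60 is Φ((60 − mean)/SD).
- Mean 75, SD 15: Φ(−1.0) = 15.9%.
- Mean 90, SD 12: Φ(−2.5) = 0.6%.

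For the limb above 120, the share is 0.01% to 2.3% over means of 75 to 90 and SDs of 12 to 15, before exclusion 5.13 is applied. The lower limb is therefore the exposed one.

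**Step 2. What if baseline is an early reading?** Let m be the mean shift from that reading to the moment before instillation, with SD s and no drug effect.
- Heart rate at least 30 above baseline: 1 − Φ((30 − m)/s). For m = 0 this is 0.1% (s = 10) to 2.3% (s = 15). For m = 10, s = 10 it is 2.3%; for m = 25, s = 15 it is 36.9%.
- SBP at least 20 below baseline, with a mean fall of m: 1 − Φ((20 − m)/s). For m = 0 this is 2.3% to 9.1%. For m = 10, s = 10 it is 15.9%; for m = 25, s = 10 it is 69.1%.

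**Step 3. What does background do to the comparison?** Let b be the share meeting a criterion before drug in each arm, and p the true new-event rate among the rest. The observed rate is b + (1 − b)p. The risk difference is the true difference times (1 − b), so 18 points becomes 0.80 × 18 = 14.4 points at b = 20%. Exact two-sided Fisher power, by full enumeration at 50 vs 50:

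| b | Observed rates, true 2% vs 20% | Power | Observed rates, true 20% vs 38% | Power |
|---|---|---|---|---|
| 0% | 2.0% vs 20.0% | 78% | 20.0% vs 38.0% | 43% |
| 5% | 6.9% vs 24.0% | 57% | 24.0% vs 41.1% | 37% |
| 10% | 11.8% vs 28.0% | 44% | 28.0% vs 44.2% | 32% |
| 20% | 21.6% vs 36.0% | 28% | 36.0% vs 50.4% | 25% |

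Example at b = 5%: 0.05 + 0.95 × 0.02 = 6.9% and 0.05 + 0.95 × 0.20 = 24.0%.

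**The case against.** Much of the opposing case stands.

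- **Outcome 6 is different.** A reader might infer that its level limbs also need no change. The text does not support that: a stable SBP of 88 is not a fall. What remains is that the size of the change is unstated, so 179 to 181 would count.
- **The upper limbs are largely guarded.** Exclusions 5.13 to 5.15 apply up to the time of the procedure. They leave open only non-persistent readings and rises during sedation or scope passage.
- **Suitable readings exist.** Heart rate is continuous and blood pressure is taken every 3 minutes. What is missing is a sentence naming which reading is baseline.
- **The window can probably be reconstructed.** A reader might infer that the 30 minutes cannot be measured. But the whole procedure is video-recorded from scope insertion and the insertion time is logged, so the time of instillation should be recoverable. The missing field is a convenience gap. Which of two instillations governs the window is still unstated.
- **Some background cannot be removed.** Sedation, biopsy and treatment of bleeding continue to act inside the window in both arms. With a higher placebo rate the fix gains less, as the second scenario shows.
- **The trial is a pilot with no power claim,** and Aim 4 is worded as exploratory.
- **A bare new-crossing rule could lose real events.** A rate of 121 before drug and 150 after is a rise of 29. The present text counts it. A new-crossing rule would not, and the 30 bpm limb misses it. The fix has to deal with this.

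**Conclusion.** The point holds for the wording of outcome 5 and for the undefined baseline in both outcomes. As written, outcome 5 counts heart rates that were present and unchanged before study drug, chiefly those below 60 bpm.

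A reader might go further and conclude that the safety comparison is biased towards a false difference, or that an epinephrine effect would be hidden. The documents support neither. With randomised, blinded arms the background is expected to be equal, so it shrinks the risk difference by the factor (1 − b) and lowers power. That is dilution.

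The size is uncertain. For b from 5% to 20%, the loss of power is 21 to 50 points if true new-event rates are 2% vs 20%, and 7 to 18 points if they are 20% vs 38%. The documents give neither b nor the event rates, and the figures treat procedures as independent although patients may contribute more than one. The direction matters because a non-significant safety result would be taken as reassuring. The change should be made: it is cheap and uses data already monitored.

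**What to change.** In Safety Outcomes, items 5 and 6:

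1. Define baseline as the last heart rate and blood pressure reading before the first instillation.
2. Count a level limb only when that reading had not already met it, that is, as a new crossing. Keep the existing thresholds.
3. Score the relative limbs against the same reading.
4. Add the clock time of each instillation to the recorded data in Procedure Performance, item 9, and state which instillation starts and which ends the 30-minute window.
5. Report by arm the maximum and minimum change from that baseline as continuous summaries, so that a further rise or fall in a patient already past a threshold is not lost.

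**Cost:** revised outcome wording, time fields on the CRF for up to two instillations, and one added summary. No new measurement is needed. **Downside:** fewer events are counted. The chosen baseline is taken with the scope in place and may itself be raised. In a patient already past a threshold, a further change smaller than the relative limb appears only in the continuous summary.
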